#### 11.7 **Progression free survival (PFS)**

Progression free survival will be defined as time from the initiation of protocol treatment to the occurrence of any of the following events: disease progression or disease recurrence or death from any cause. All patients surviving at the time of analyses without events will be censored at their last follow-up date.

PFS along with the confidence intervals will be estimated using the Kaplan-Meier method. Patients with local calls of disease progression (i.e. calls made by the treating institution), will be counted as having had an event, even if the central review does not declare progression. We will also report PFS based on central radiology review as a secondary analysis, if adequate number of disagreements in progressions exist between the treating institutions and the central radiology review to make such an analysis meaningful.

#### 11.8 Pharmacokinetic and Correlative Studies

A descriptive analysis of pharmacokinetic (PK) parameters of LOXO-101 (larotrectinib) will be performed to define systemic exposure, drug clearance, and other pharmacokinetic parameters. The PK parameters will be summarized with simple summary statistics, including means, medians, ranges, and standard deviations (if numbers and distribution permit).

All these analyses will be descriptive and exploratory and hypotheses generating in nature.

A descriptive analysis of the exploratory aims described in [Section 1.3](#) will be performed and will be summarized with simple summary statistics. All of these analyses will be descriptive in nature.

#### 11.9 Gender and Minority Accrual Estimates

The gender and minority distribution of the study population is expected to be:

Racial category	Ethnicity				Total
	Not Hispanic or Latino		Hispanic or Latino		
	Female	Male	Female	Male	
American Indian/Alaska Native	0	0	0	0	0
Asian	1	1	0	0	2
Native Hawaiian or Other Pacific Islander	0	0	0	0	0
Black or African American	3	5	0	0	8
White	12	20	4	2	38
More than one race	1	0	0	0	1
Total	17	26	4	2	49

This distribution was derived from the demographic data for patients enrolled on recent COG Phase 2 trials.

### 12.0 EVALUATION CRITERIA

#### 12.1 Common Terminology Criteria for Adverse Events (CTCAE)

The descriptions and grading scales found in the current version of the NCI Common Terminology Criteria for Adverse Events v5.0 (CTCAE) will be utilized for AE reporting. All appropriate treatment areas should have access to a copy of the current CTCAE v5.0. A copy of the CTCAE v5.0 can be downloaded from the CTEP website

(<http://ctep.cancer.gov>).

## 12.2 Progression-Free Survival

Progression-free survival (PFS) is defined as the duration of time from start of subprotocol treatment to time of progression or death, whichever occurs first.

Development of new disease or progression in any established lesions is considered progressive disease, regardless of response in other lesions – e.g., when multiple lesions show opposite responses, the progressive disease takes precedence.

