## 10.0 CRITERIA FOR REMOVAL FROM PROTOCOL THERAPY AND OFF STUDY CRITERIA

### 10.1 Criteria for Removal from Protocol Therapy

- a) Clinical (including physical examination or serum tumor markers) or radiographic evidence of progressive disease (See [Section 12](#)).
- b) Adverse Events requiring removal from protocol therapy (See [Section 6](#)).
- c) Refusal of protocol therapy by patient/parent/guardian
- d) Non-compliance that in the opinion of the investigator does not allow for ongoing participation.
- e) Completion of 26 cycles of therapy.
- f) Physician determines it is not in the patient's best interest.
- g) Repeated eligibility laboratory studies (CBC with differential, bilirubin, ALT (SGPT) or serum creatinine) are outside the parameters required for eligibility prior to the start of protocol therapy (See [Section 8.1](#)).
- h) Study is terminated by Sponsor.
- i) Pregnancy
- j) Patient did not receive protocol treatment after study enrollment.

**Patients who are removed from protocol therapy during cycle 1 should continue to have the required observations in [Section 8.1](#) until the originally planned end of the cycle or until all adverse events have resolved per [Section 13.4.4](#), whichever happens LATER. The only exception is with documentation of the patient's withdrawal of consent from the APEC1621SC screening protocol. Patients who are removed from protocol therapy in subsequent cycles should have the necessary observations to ensure adequate clinical care.**

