## 12.3 Response Criteria for Patients with Solid Tumors

See the table in [Section 8.0](#) for the schedule of tumor evaluations. Eligible patients must have measurable disease present at baseline and have had their disease re-evaluated after at least one dose of protocol therapy. In addition to the scheduled scans, a confirmatory scan should be obtained on the next consecutive cycle following initial documentation of objective response.

As outlined, patients will be assigned to one of the following categories for assessment of response: a) solid tumor (non-CNS) and measurable disease ([Section 12.4](#)); b) neuroblastoma with MIBG positive lesions ([Section 12.5](#)); c) CNS tumor ([Section 12.7](#)); and d) non-Hodgkin lymphoma/histiocytosis ([Section 12.8](#)). Note: Neuroblastoma patients who do not have MIBG positive lesions should be assessed for response as solid tumor patients with measurable disease.

Response and progression will be evaluated in this study using the revised Response Evaluation Criteria in Solid Tumors (RECIST) guideline (version 1.1). Key points are that 5 target lesions are identified and that changes in the *largest* diameter (unidimensional measurement) of the tumor lesions but the *shortest* diameter of malignant lymph nodes are used in the RECIST v 1.1 criteria.

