#### Progressive Disease (PD):

At least a 20% increase in the sum of the diameters of target lesions, taking as reference the smallest sum on study (this includes the baseline sum if that is the smallest on study). In addition to the relative increase of 20%, the sum must also demonstrate an absolute increase of at least 5 mm. (Note: the appearance of one or more new lesions is also considered progressions). Note: in presence of SD or PR in target disease but unequivocal progression in non-target or non-measurable disease, the patient has PD if there is an overall level of substantial worsening in non-target disease such that the overall tumor burden has increased sufficiently to merit discontinuation of therapy

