### 12.4.2 Evaluation of Non-Target Lesions

#### Complete Response (CR):

Disappearance of all non-target lesions and normalization of tumor marker level. All lymph nodes must be non-pathological in size (<10 mm short axis)

Note: If tumor markers are initially above the upper normal limit, they must normalize for a patient to be considered in complete clinical response.

Non-CR/Non-PD:

Persistence of one or more non-target lesion(s) and/or maintenance of tumor marker level above the normal limits

Progressive Disease (PD):

Appearance of one or more new lesions and/or *unequivocal progression* of existing non-target lesions. *Unequivocal progression* should not normally trump target lesion status. It must be representative of overall disease status change, not a single lesion increase.

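### For non-CNS solid tumors with more than one lesion, Section 12.2 defines PFS progression lesion by lesion while Section 12.4 defines it by the target sum and overall non-target status, and nothing says which governs.

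*Combined protocol and SAP*

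**What the plan says.** Section 12.2 (Progression-Free Survival) is not limited to any tumor type. It defines PFS as time from the start of treatment to progression or death, and then says: "Development of new disease or progression in any established lesions is considered progressive disease, regardless of response in other lesions". For mixed responses it adds that "when multiple lesions show opposite responses, the progressive disease takes precedence". It states no size of change that makes a single lesion progressive.

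Section 12.3 says: "Response and progression will be evaluated in this study using the revised Response Evaluation Criteria in Solid Tumors (RECIST) guideline (version 1.1"). It assigns non-CNS solid tumors with measurable disease to Section 12.4. In 12.4.1, target progression is: "At least a 20% increase in the sum of the diameters of target lesions, taking as reference the smallest sum on study". In addition, "the sum must also demonstrate an absolute increase of at least 5 mm". New lesions also count. If target disease is stable or responding, "the patient has PD if there is an overall level of substantial worsening in non-target disease". Section 12.4.2 says of unequivocal progression in non-target lesions: "It must be representative of overall disease status change, not a single lesion increase".

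Section 11.7 counts a local progression call as a PFS event even if central review does not declare progression. PFS by central review is a secondary analysis, done only if there are enough disagreements to make it meaningful. The any-lesion sentence of 12.2 appears again, word for word, in the CNS criteria (12.7.4).

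**The concern.** A sum rule lets shrinkage in one lesion offset growth in another. The mixed-response clause in 12.2 forbids that offset. Both rules are stated for the same patients, and no passage ranks them. Two sites reading the same scan could each follow the protocol, yet one would record progression and the other stable disease or partial response.

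PFS is a secondary aim (1.2.1). Because local calls are the events, central review does not correct the difference in the main PFS analysis. Section 10.1(a) lists as a reason for removal "Clinical (including physical examination or serum tumor markers) or radiographic evidence of progressive disease" and points to Section 12 as a whole, so the ambiguity also reaches removal from protocol therapy.

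**Working it through.** The plan gives no figure on this point to reproduce. The check applies both rules to the same measurements, which are hypothetical. The 20%, 5 mm and 30% thresholds are those of 12.4.1. Since 12.2 has no lesion threshold, I borrow 20% and 5 mm for a single lesion; that is an assumption.

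**Case A, responding sum with one growing lesion.** Targets go from 50/40/20 mm to 25/20/26 mm.
- Sum: 50 + 40 + 20 = 110 mm; 25 + 20 + 26 = 71 mm. Change = (71 − 110)/110 = −35.5%. Under 12.4.1 this is partial response, since the fall is at least 30%.
- Third lesion: (26 − 20)/20 = +30%, +6 mm, while the other two fell 50%. Under 12.2 this is progression.

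**Case B, stable sum with one growing lesion.** Targets go from 40/40 mm to 40/50 mm.
- Sum: 80 to 90 mm, 10/80 = +12.5%, +10 mm. The 5 mm condition is met but the 20% condition is not: stable disease under 12.4.1.
- Second lesion: 10/40 = +25%, +10 mm: progression under 12.2.

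**Non-target disease.** If one of several non-target lesions progresses and overall disease status is unchanged, 12.4.2 does not call progression. Section 12.2 can.

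**Single lesion.** The sum is the lesion, so with the same threshold the two rules agree.

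**What one disagreement does to a PFS date.** Section 8.1 schedules tumor evaluation every other cycle three times, then every three cycles, with 28-day cycles. If progression is called one scheduled evaluation earlier, the event moves by 2 × 28 = 56 days, or later by 3 × 28 = 84 days. If the sum never meets 12.4.1, the difference is between an event and a patient still at risk.

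**How often the rules could disagree.** The documents give no mixed-response rate and no lesion counts, so this is illustration only. Assumptions: one scan compared with baseline, baseline diameters uniform on 15–50 mm, normally distributed percentage change with SD 10%, 15% or 20%, the borrowed lesion threshold, and 200,000 simulated patients per setting. Entries are the percentage of patients classified differently by the two rules, over that SD range.

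| Assumed mean change and correlation between lesions | 1 target | 2 targets | 5 targets |
|---|---|---|---|
| Mean 0, independent | 0 | 3.5–18.5 | 9–52 |
| Mean 0, correlation 0.8 | 0 | 1.4–6 | 4–15 |
| Mean −30%, independent | 0 | 0–1.0 | 0–2.6 |

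Disagreement grows with the number of targets. It shrinks when lesions move together or when most of them respond.

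**The case against.** The best reply is that 12.3 settles the matter: it names RECIST 1.1 for both response and progression and routes these patients to 12.4, while 12.2 cannot be applied alone because it has no threshold. This is probably the intent, and it makes 12.4 the more likely reading at many sites. It does not remove the conflict. Section 12.3 does not say that it overrides 12.2, and 12.2 is where a reader looks for PFS. Nor can progression in a lesion simply be read as progression under 12.4.1, because 12.4.1 defines progression only for the target sum. On that reading the mixed-response clause would have no effect among target lesions.

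Several stronger readings are tempting, and the objection is right about them.
- A reader might infer that any growth in one lesion is progression under 12.2. The text says progression in a lesion, without defining it.
- A reader might take the bar on single-lesion increases as a rule for all lesions. In 12.4.2 it covers non-target disease only; for targets the conflict is with the sum rule.
- A reader might infer that the primary response rate is directly affected. Under 12.4.4 and 12.9, best response comes from the sequence of overall assessments, which for these patients follow the table in 12.4.3. Sections 11.5 and 12.3.1.1 require central confirmation of a response. What remains is indirect: 12.9 requires two determinations of partial response or better to precede progression, so an early progression call could cut the sequence short.
- A reader might take the upper simulated figures as the expected effect. They need five independently changing targets with no average shrinkage, whereas Section 2.4 reports confirmed partial response in six of seven evaluable patients with fusion-positive tumors.

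**Conclusion.** The conflict stands for non-CNS solid tumors with more than one lesion. A mixed response can be progression under 12.2 and stable disease or partial response under 12.4, and PFS events and dates then depend on the section followed. The contradiction rests on the text alone. Cases A and B also need a lesion-level threshold, which I borrowed from 12.4.1.

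Its effect on PFS or on the response rate cannot be computed from the documents. Per-scan disagreement from about 0% to over 50% is a range over assumptions, not an estimate. With a primary cohort of 20, a few differently dated events could visibly move the Kaplan-Meier curve. The documents do not support a claim that the primary decision rule fails. This is an endpoint definition that should be corrected because the correction is cheap.

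**What to change.** Reconcile 12.2 with 12.3, 12.4.1 and 12.4.2. For the PFS analysis, replace the any-lesion sentence and its mixed-response clause in 12.2 with text such as:

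*For the PFS analysis, radiographic progression is determined by the disease-specific criteria in Sections 12.4 to 12.8, and new lesions count as progression. Progression called on clinical or laboratory grounds without imaging also counts as an event.*

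The second sentence is needed because Section 8.1 (footnote 4) and 10.1(a) allow progression to be called without imaging; a purely radiographic definition would create a new conflict. Reconcile the identical sentence in 12.7.4 in the same amendment.

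How 10.1(a) applies to removal from therapy must be reconciled with these passages by the clinical team. No rule is proposed here.

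Cost: a short text change in the next amendment, with no added scans or patients. The study was activated in July 2017, so progression calls already made may need a check of which rule was used.

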#### 12.7.3 Selection of Target and Non-Target Lesions

For most CNS tumors, only one lesion/mass is present and therefore is considered a “target” for measurement/follow up to assess for tumor progression/response. If multiple measurable lesions are present, up to 5 should be selected as “target” lesions. Target lesions should be selected on the basis of size and suitability for accurate repeated measurements. All other lesions will be followed as non-target lesions. The lower size limit of the target lesion(s) should be at least twice the thickness of the slices showing the tumor to decrease the partial volume effect (e.g., 8 mm lesion for a 4 mm slice).

Any change in size of non-target lesions should be noted, though does not need to be measured.

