#### 12.7.4 Response Criteria for Target Lesions

Response criteria are assessed based on the product of the longest diameter and its longest perpendicular diameter. Development of new disease or progression in any established lesions is considered progressive disease, regardless of response in other lesions – e.g., when multiple lesions show opposite responses, the progressive disease takes precedence. Response Criteria for target lesions:

- **Complete Response (CR):** Disappearance of all target lesions. Off all steroids with stable or improving neurologic examination.
- **Partial response (PR):**  $\geq 50\%$  decrease in the sum of the products of the two perpendicular diameters of all target lesions (up to 5), taking as reference the initial baseline measurements; on a stable or decreasing dose of steroids with a stable or improving neurologic examination.

- **Stable Disease (SD):** Neither sufficient decrease in the sum of the products of the two perpendicular diameters of all target lesions to qualify for PR, nor sufficient increase in a single target lesion to qualify for PD; on a stable or decreasing dose of steroids with a stable or improving neurologic examination.
- **Progressive Disease (PD):** 25% or more increase in the sum of the products of the perpendicular diameters of the target lesions, taking as reference the smallest sum of the products observed since the start of treatment, or the appearance of one or more new lesions.

Increasing doses of corticosteroids required to maintain stable neurological status should be strongly considered as a sign of clinical progression unless in the context of recent wane or transient neurologic change due e.g. to radiation effects.

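### Section 12.2 and the opening of 12.7.4 make growth of any one lesion progression, 12.4.1 and the CNS progression bullet use the sum over target lesions, and no sentence expressly ranks the two rules

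*Combined protocol and SAP*

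**What the plan says.** Two progression rules appear in Section 12.

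- **Any-lesion rule.** Section 12.2, which covers all tumour types, states: "Development of new disease or progression in any established lesions is considered progressive disease, regardless of response in other lesions". It adds that progressive disease wins when lesions move in opposite directions. It gives no size threshold for a single lesion. For CNS tumours the opening of 12.7.4 repeats it: "Development of new disease or progression in any established lesions is considered progressive disease".
- **Sum rule.** For solid tumours, 12.4.1 requires "At least a 20% increase in the sum of the diameters of target lesions, taking as reference the smallest sum on study", plus an absolute increase of 5 mm. For non-target disease, 12.4.2 says of unequivocal progression: "It must be representative of overall disease status change, not a single lesion increase". For CNS tumours the progression bullet of 12.7.4 requires "25% or more increase in the sum of the products of the perpendicular diameters of the target lesions", or a new lesion.

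The stable-disease bullet of 12.7.4 uses single-lesion wording: "nor sufficient increase in a single target lesion to qualify for PD".

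Three other places bear on how much this matters. Section 12.3 names RECIST 1.1 for both response and progression. Section 11.7 counts a progression call by the treating institution as a PFS event even when central review disagrees. Section 10.1(a) removes a patient from therapy for progressive disease and refers to Section 12 as a whole, so to both rules.

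**The concern.** When a patient has several lesions and one grows while the rest shrink or hold still, the two rules can give different answers for one scan. Outside CNS the conflict is between the PFS definition (12.2) and the response criteria (12.4.1 and 12.4.2). In CNS it lies inside one section.

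Three things depend on the answer:

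- **PFS**, the first secondary aim. Because local calls count, differences between sites in the rule they follow pass straight into the main PFS analysis. The any-lesion rule gives earlier events and lower PFS.
- **Treatment.** The same scan could take a child off the drug at one site and not at another.
- **Individual CNS response calls, possibly.** Section 12.9 needs two determinations of partial response or better before progression. A CNS mixed response that the bullets class as a partial response is progression by the opening sentence.

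**Working it through.** The point disputes no figure in the plan, so there is none to reproduce. The check asks whether the rules really disagree on the same scan, and by how much. Lesion sizes below are assumed. Section 12.2 gives no per-lesion threshold, so I also assume that the percentage (and the 5 mm outside CNS) written for the sum applies to each lesion. Baseline is taken as the smallest earlier measurement.

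**Step 1. How far must one lesion grow?** Let lesion *a* grow while lesion *b* stays the same.

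- Non-CNS, any-lesion: progression at max(1.2a, a + 5). Sum: max(1.2(a + b), a + b + 5) − b.
- CNS, square lesions, any-lesion: side √(1.25a²). Sum: side √(1.25(a² + b²) − b²).

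| Baseline *a* and *b* | Any-lesion rule | Sum rule |
|---|---|---|
| Non-CNS, 10 and 60 mm | max(12, 15) = 15 mm | 84 − 60 = 24 mm |
| Non-CNS, 30 and 30 mm | max(36, 35) = 36 mm | 72 − 30 = 42 mm |
| CNS, 12×12 and 30×30 mm | √180 = 13.4 mm | √(1305 − 900) = 20.1 mm |
| CNS, 20×20 and 20×20 mm | √500 = 22.4 mm | √(1000 − 400) = 24.5 mm |

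The gap is widest when a small lesion grows beside a large one.

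**Step 2. Mixed response.**

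- Non-CNS, 60 to 30 mm and 10 to 16 mm: the sum goes from 70 to 46, and 46/70 − 1 = −34.3%. That is a partial response by 12.4.1, where the threshold is −30%. The small lesion grows by 16/10 − 1 = +60% and 6 mm, which is progression by 12.2.
- CNS, 30×30 to 15×15 and 12×12 to 15×15: the sum goes from 1044 to 450, and 450/1044 − 1 = −56.9%. That is a partial response by the bullet, where the threshold is −50%, if steroids and examination permit. The small lesion grows by 225/144 − 1 = +56.3%, which is progression by the opening sentence.

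**Step 3. CNS, one lesion growing and the other unchanged.** 30×30 unchanged, 12×12 to 14×14: the sum changes by 1096/1044 − 1 = +5.0%, below 25%, so this is not progression by the progression bullet. The small lesion grows by 196/144 − 1 = +36.1%, so it is progression by the opening sentence.

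**Step 4. Where the rules agree.** With a single lesion the sum is that lesion, so the rules coincide. A new lesion is progression under both. Section 12.7.3 says: "For most CNS tumors, only one lesion/mass is present". The conflict is therefore confined to patients with two or more lesions that behave differently.

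**Step 5. Size on PFS.** If the two rules put a patient's event on opposite sides of a landmark time, the PFS estimate there moves by 1/N, absent earlier censoring: 100/20 = 5.0 points for the primary cohort, 100/41 = 2.4 with all 21 expansion patients added, and 100/49 = 2.0 at the enrolment ceiling. It moves by 0 if both dates fall on the same side. The number of such patients cannot be derived from the documents.

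**The case against.** The best defence is that 12.2 was never meant as a measurement rule. Section 12.3 names RECIST 1.1 for progression in this study and 12.4.1 supplies the thresholds. On this view 12.2, which has no threshold, only says that progression in one component overrides response elsewhere, as the overall-response tables already do when non-target disease progresses or a new lesion appears.

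Much of that stands outside CNS, where 12.3 does favour the sum rule. It does not settle the matter. The illustration in 12.2 concerns single lesions moving in opposite directions, not components, and nothing subordinates 12.2 to 12.3. Nor can RECIST decide the CNS case, because 12.7.4 measures products of two diameters and carries the any-lesion sentence itself.

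It is also fair to say that choosing the sum rule is a judgement. Within 12.7.4 the opening sentence and the stable-disease wording both lean towards single lesions. I prefer the sum because it is the only rule with a stated threshold and it agrees with 12.3, 12.4.1 and the CNS progression bullet.

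Finally, the examples are illustrative. The lesion sizes and per-lesion thresholds are assumed, and the 5-point bound is what reclassifying any one of 20 patients would give. That is accepted.

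**Conclusion.** The conflict is real and worth correcting, but narrow. The same multi-lesion scan can be a partial response or stable by one part of Section 12 and progression by another, and no sentence expressly says which prevails. The contradiction between 12.2 and 12.4.2 needs no assumed threshold; the numerical examples do. PFS is a secondary estimate with no decision threshold, and each affected patient moves a landmark estimate by 0 to 5 points at N=20.

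A reader might infer more than the documents support:

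- *That some CNS scans with one growing lesion are neither stable nor progressive, leaving the child barred from the next cycle by 5.2 but not removable under 10.1(a).* This requires ignoring the opening sentence of 12.7.4, which makes such a scan progression, and reading an unstated 25% per-lesion threshold into the stable-disease bullet. Section 10.1 also allows removal for clinical progression or on the physician's judgement.
- *That 12.2 is the only rule for growth of MIBG-positive lesions.* For local calls, 12.5.2 already classes an unchanged number of positive lesions as stable. Only a relative score above 1.0 without new lesions, on the central scale in 12.5.3, is left unclassed.
- *That the choice of rule shifts the progression date by at least a full scan interval.* The evaluation schedule in 8.1 lets the investigator call progression on clinical or laboratory grounds without a scan, so the shift can be shorter.
- *That the primary decision is compromised.* Single CNS mixed responses could be called differently, but no effect on the rule of 3 responses in 20 is shown.

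**What to change.** 1. In 12.2, replace the any-lesion sentence with: *progression is overall progressive disease under the applicable disease-specific criteria (12.4 to 12.8), or clinical progression declared by the investigator*.
2. In 12.7.4, delete the opening any-lesion sentence and base the size condition of the stable-disease bullet on the sum of products over all target lesions, as in the progression bullet. New lesions and unequivocal non-target progression remain progressive disease under 12.7.5 and 12.7.7.
3. Optionally, state in 12.5.3 how a relative score above 1.0 without new lesions is classed on central review.

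The cost is wording only: no added scans, readers or patients. The downside is that a child with one small growing lesion may stay on the drug longer, and PFS may be slightly higher, unless the investigator declares clinical progression. The change leaves the steroid and neurological conditions in the CNS stable-disease bullet as they are.
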